**Clinical investigation of a new nanohybrid resin composite Venus Pearl in class 2
cavities– a multi-center study**

NCT01925040

Study Protocol and Statistical Analysis Plan

Date 15.08.2013

Objective of the study

The objective of this study is to compare the performance of the composite resin Venus Pearl (a development based on the material "Venus Diamond", Heraeus Kulzer, Hanau-Germany) and the commercially available control material Filtek Supreme XTE (3M/ESPE, Seefeld-Germany- available for the study center in Germany) and its equivalent material Filtek Supreme Ultra (3M/ESPE, Seefeld-Germany- available for the study center in the United States) for the restoration of class II-cavities. Primary endpoints of the study are: loss of the restoration, fracture of the restoration, postoperative sensitivity, marginal discoloration and marginal gap or step formation. Secondary endpoints are the evaluation of secondary caries, plaque accumulation and gingival reactions.

Ethics

The study is in accordance with the declaration of Helsinki. The study protocol will be assessed and approved by the ethical committee of Hannover Medical School as well as by the Institutional Review Board of the Oregon Health and Science University (OHSU). Each patient will receive a detailed information leaflet and has to declare in writing her or his consent to participate in the study. This written informed consent can be cancelled by the patient at any time without justification.

Study design

The study will be executed as a multi-center, single-blinded and randomized clinical investigation.

Multicenter, single-blinded, and randomized clinical investigation. Study sites are the Department of conservative Dentistry, periodontology and Preventive Dentistry at the Hannover Medical School, Hannover, Germany, and the Department of Restorative Dentistry at the Oregon Health and Science University, Portland, Oregon, USA. Coordination of the study at both study sites is done by the Hannover Medical School.

General information

Time frame of the study: 2 years (with optional extension to 4 years)

Number of patients/ restorations: 90 comparable cavities per Institution (180 total), randomization

Test material: n=90 (n = 45 per site)

Control material: n=90 (n = 45 per site)

Recruitment of patients

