Patients will be recruited by the Department of Conservative Dentistry, Periodontology and Preventive Dentistry of the Hannover Medical School and the Department of Restorative Dentistry of the Oregon Health and Science University (OHSU). Patients who require a class II restoration will be included in the study (see inclusion criteria). Each patient will be eligible to receive up to four restorations, with either a test or a control material. Patients will be given detailed information regarding the study before they are included in the study. Patients will receive an information leaflet and a copy of their signed informed consent form. Patients, who could not follow their examination appointments, will be contacted by phone to arrange a new appointment. Patients who miss three appointments will be classified as "drop-outs", which means that no further appointments will be scheduled for these patients regarding this study.

Inclusion criteria

- Patients should be 18 years and older.
- Study teeth should have an interproximal (Class II) carious lesion or an existing defective class II restoration requiring restorative therapy on premolars or molars.
- The maximum cavity depth determined by the radiograph will be D2 (Tyas classification).
- The teeth included in the study need to have a proximal contact with the adjacent tooth and be in occlusion with the opposing dentition.
- The teeth included in the study should be vital with no signs of pulpal pathology.
- Patients that report brushing regularly without severe gingival inflammation and/or extensive caries.
- Patients should have no allergies or systemic diseases which inhibit the treatment.
- Patients should have voluntary participation and sign a written informed consent form.
- Patients should be willing to participate in the recall/re-examination appointments.

Exclusion criteria

- Simultaneous participation in another study about dental restorative materials.
- Written informed consent form not signed.
- Nonvital pulp / periapical lesion.
- Insufficient oral hygiene despite detailed instructions.
- Pregnancy/ breast feeding before placement of the study restoration.
- Minors.
- Severe malocclusion/ malalignment/ traumatic occlusion/ bruxism.
- Known allergy to any components present in any of the materials that are used for this study.
- Unclear mucosal alterations, e.g. oral lichenoid reactions/lesions.

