Secondary endpoints are the evaluation of secondary caries, plaque accumulation and gingival reactions and the comparison of the primary score at week 1, month 6, month 12 and month 24 after restoration. Beside this, the single components of the three categories of the primary endpoints will be compared.

Randomization, stratification and blinding

This is an observer-blind clinical trial, e.g. evaluators will not know the given treatment. Restorations will be distributed evenly between the control and the experimental groups using randomization lists.

The application of the two restorative materials is limited to premolars and molars and to achieve a uniform distribution of both tooth types, stratification with the strata premolar and molar will be performed in the randomization process. In addition randomization will be stratified by center.

Randomization will be performed centrally by the Institute of Biometrics to ensure admission before allocation. The randomization will not be based on patients' names, rather than on a scheduled visit, to avoid problems with patients that do not show up for the treatment.

In order to guarantee an objective evaluation at the different time points, the Case Report Form has separate sections for each evaluation, so that the evaluators only use the form for the present examination. Through this method, the evaluator cannot see which assessment he/she gave during previous examinations. These sections will only have the patient number information.

The treatment allocation and the corresponding patient ID will be kept in a separate file that is inaccessible for operators and evaluators.

Description of the primary analysis and key secondary analysis

In the primary analysis the superiority of Venus Pearl will be investigated. Therefore the primary analysis will be conducted on the ITT population, e.g. in all randomized patients. The missing values will be replaced as described below. For the comparison of the scores of the Venus Pearl and Filtek Supreme group an ANOVA will be performed 24 months after restoration. Here, center, tooth type and treatment will be incorporated as covariables. The study is successful if the 95 % confidence interval for the treatment effect (Venus Pearl – Filtek Supreme) is below 0.

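### Materials are not balanced within patients who may have up to four study teeth, and the unit of randomisation is unclear; this costs precision and, if a patient's teeth share one allocation, error control

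*Combined protocol and SAP*

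**What the plan says.** Recruitment of patients states: "Each patient will be eligible to receive up to four restorations, with either a test or a control material". General information counts the size in cavities: "Number of patients/ restorations: 90 comparable cavities per Institution (180 total), randomization", with 90 per material and 45 per material at each site. No number of patients and no distribution of teeth per patient is given.

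Randomization, stratification and blinding states: "Restorations will be distributed evenly between the control and the experimental groups using randomization lists". On strata it says: "stratification with the strata premolar and molar will be performed in the randomization process. In addition randomization will be stratified by center". No rule pairs, blocks or balances materials within a patient, and no block size is given.

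Three units appear. The lists distribute restorations. The same section ties randomisation to a scheduled visit, so that patients who do not attend cause no problem. The primary analysis set is defined in terms of patients randomised, and the statistical Study design section sums the primary score per patient.

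The primary ANOVA at 24 months contains centre, tooth type and treatment, with no patient term. Success requires the 95% confidence interval for the treatment difference to lie below 0. Mixed models are named only as a sensitivity analysis, and their random effects are not specified.

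**The concern.** Teeth in one mouth share hygiene, diet and bite. The plan itself treats such factors as relevant: eligibility screens on hygiene, gingival inflammation and bruxism, and the primary score has a biological part. A positive correlation between scores from the same patient is therefore a reasonable assumption.

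With two or more study teeth, comparing the materials inside one mouth removes what those teeth share. A patient who receives only one material contributes solely through comparison with other patients, which carries all the between-patient variation. Several restorations from one patient in the same arm can also unbalance the arms on patient characteristics by chance. Success rests on one confidence interval and the plan states no power calculation, so there is no documented margin from which to give precision away.

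**Working it through.** The inputs from the documents are the 180 restorations, the 1:1 split, up to four teeth per patient, the two strata and the ANOVA terms. The within-patient correlation (rho), the block size and the teeth per patient are not given and are assumed below.

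1. Stated size. 45 × 2 sites = 90 per material, and 90 × 2 = 180, as stated. The number of patients could lie anywhere from 46 (90/4 = 22.5, so 23 per centre) to 180.

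2. Chance that a patient receives one material only.
   - Independent 1:1 allocation of m teeth: 2 × 0.5^m, which is 50% for two teeth, 25% for three and 12.5% for four.
   - Two consecutive teeth on one permuted-block list of block size b, starting at a random place: ((b−1)/b) × ((b/2−1)/(b−1)) + 0.5/b. This gives 25% for b = 2, 37.5% for b = 4, 41.7% for b = 6 and 43.8% for b = 8.
   - One premolar and one molar, on separate lists: 50%.
   - One allocation per patient: 100%. One per visit: 100% of patients whose teeth are all restored at one visit.

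3. Information on the treatment effect when the model has a patient effect. Code treatment as ±0.5, let S be the sum of the codes within a patient, and assume equal correlation rho between teeth. In units of 1/SD², the information per patient is [m/4 − rho × S²/(1 + (m−1)rho)]/(1 − rho).
   - Two teeth, one of each material (S = 0): 0.5/(1 − rho). Two teeth, same material (S = ±1): 0.5/(1 + rho). Average under independent allocation: 0.5/(1 − rho²). Balanced over independent = 1 + rho. Balanced over one allocation per patient = (1 + rho)/(1 − rho).
   - Three teeth (S² = 1/4 if balanced, 3/4 on average if independent): (3 + 5rho)/(3 + 3rho).
   - Four teeth (S² = 0 if balanced, 1 on average if independent): (1 + 3rho)/(1 + 2rho).

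| Assumed rho | Two teeth, balanced vs independent | Three teeth | Four teeth | Two teeth, balanced vs one allocation per patient |
|---|---|---|---|---|
| 0.2 | 1.20 | 1.11 | 1.14 | 1.50 |
| 0.3 | 1.30 | 1.15 | 1.19 | 1.86 |
| 0.5 | 1.50 | 1.22 | 1.25 | 3.00 |

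4. Behaviour of the planned ANOVA, which has no patient term.
   - Restorations allocated independently: the correlation cancels on average and the test stays approximately valid.
   - One allocation per patient: the true variance is larger by 1 + (m−1)rho. At rho = 0.3 this is 1.3 for two teeth, and the two-sided error is 2 × [1 − Φ(1.96/√1.3)] = 8.6%. For four teeth it is 1.9, and the error is 15.5%.
   - Two teeth, one of each material: the true variance is smaller by 1 − rho = 0.7, which the ANOVA does not see. The interval is too wide, and the two-sided error is 2 × [1 − Φ(1.96/√0.7)] = 1.9%.

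5. Illustration of power. Assume 90 patients with two teeth each, rho = 0.3 and a true difference of 0.42 SD. That is the difference detectable with about 80% power if all 180 observations were independent: (1.96 + 0.84) × √(2/90) = 0.42. The standard error is 1/√(90 × information).
   - Independent allocation, planned ANOVA: information 0.5, SE 0.149, power Φ(0.42/0.149 − 1.96) = 80%.
   - Independent allocation, patient effect: information 0.549, SE 0.142, power 84%.
   - Balanced allocation, planned ANOVA: true SE 0.125, effective critical value 1.96/√0.7 = 2.34, power Φ(0.42/0.125 − 2.34) = 85%.
   - Balanced allocation, patient effect: information 0.714, SE 0.125, power 92%.

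**The case against.** The strongest reply is that this is an efficiency preference whose size rests on unknowns, and whose gain does not reach the planned success criterion because that ANOVA has no patient term. The second part stands: in the illustration, balance alone moves power from 80% to 85%, not 92%, and makes the test conservative. The remedy must therefore change the model as well as the allocation. The first part stands as a limit on size. Teeth per patient and rho are unknown, 46 patients is the extreme case, and the eligibility criteria exclude poor hygiene, bruxism, xerostomia and extensive caries, which narrows differences between patients.

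A reader might infer three stronger things that the documents do not support.
- That half of two-tooth patients will certainly receive one material. This holds for independent allocation per tooth. Under block lists or a different unit the share runs from 25% to 100%.
- That the within-mouth comparison is lost to the trial. Under independent allocation, 50% of two-tooth, 75% of three-tooth and 87.5% of four-tooth patients still receive both materials, and a model with a patient effect can use them.
- That the result is biased. Chance imbalance under independent randomisation is not bias, and the interval allows for it.

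Two practical objections also stand. Drawing all of a patient's teeth at enrolment would conflict with the visit-based randomisation that the plan chose because of non-attendance. Also, the sentence that allows up to four restorations does not say plainly whether one patient may receive both materials.

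**Conclusion.** The point holds as a loss of precision and of chance balance, joined to an undefined unit of randomisation. It is worth correcting before the lists are used. For any positive within-patient correlation, balancing within patient gains information from every patient with two or more study teeth, provided that the primary model includes the patient. Single-tooth patients are unaffected, so the gain for the whole trial depends on a mix of patients that the plan does not state.

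The more serious consequence is conditional. The planned test exceeds its nominal 5% only if the teeth of one patient share an allocation. The documents neither state nor exclude this.

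**What to change.** In Randomization, stratification and blinding:
- State that the restoration is the unit, and bring the definitions of the analysis set and the score into line with it. State also whether a patient may receive both materials; the rules below presuppose this.
- When two or more study teeth of a patient are to be restored at the same scheduled visit, draw their allocations in one central call, split evenly with a difference of at most one. Choose at random which material has the majority when the number is odd, and which tooth receives which material.
- For teeth restored at a later visit, use a central draw weighted towards the material of which the patient has less, so that the allocation is not predictable.
- Keep centre and tooth type as strata for single-tooth patients.

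In the description of the primary analysis, keep centre and tooth type as covariates for all restorations and add a patient random effect. Without it the gain is largely not realised and the interval is too wide.

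The cost is reprogramming the central randomisation before first use and a slightly looser balance on tooth type. There is also a side effect: Assessment of restorations excludes the affected patient after certain treatment-related events, and with both materials in one mouth such an exclusion will more often remove restorations from both arms. No additional patients are needed.

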- Severe medical complications (organ transplants, cancer, immune-compromised, long-term antibiotic or steroid therapy).
- Infectious diseases such as HIV/Aids, Hepatitis, etc.
- Application of bleaching products less than 14 days before placement of the restoration.
- Orthodontic treatment during the study.
- Xerostomia.
- Untreated periodontal diseases.
- Rampant or extensive caries present.
- Systemic diseases with potential oral manifestation.
- Sufficient isolation according to the criteria of adhesive techniques not possible, e.g. application of rubber dam.
- Direct adhesive restoration not indicated.
- Replacement of more than one cusp indicated.
- Dental fears patients.
- Cracked tooth syndrome in study tooth.

Assessment of restorations

Restorations will be assessed by the evaluator per site at baseline (1 week after placement), as well as after 6, 12 and 24 months. Evaluations will be documented within the source data (patient's documentation) and in the Case Report Form (CRF).

Photographs of the teeth will be taken after the cavity preparation and after the restoration has been placed and finished as well as at each evaluation appointment.

If the study will be extended to 4 years, two additional assessments will be done, after 3 and 4 years (36 and 48 months) and patients will be informed of a possible request for recall at years 3 and 4 at the initiation of the study.

The evaluations will be based on the Recommendations for Conducting Controlled Clinical Studies of Dental Restorative Materials, Science Committee Project 2/98 - FDI World Dental Federation (J Adhes Dent 9 (1), 121-147 (2007)).

Partial impressions of the study teeth will be taken at baseline and during all subsequent examinations of the restorations with an addition-type silicone material (Flexitime Putty and Correct Flow, Heraeus, Hanau-Germany) and a plastic inlay tray. These impressions will be used to determine the in-vivo wear of the restorations by means of replica using a resin material (DuroCit, Struers, Willich-Germany) by means of scanning electron microscopic-warden images.

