Side effects that are associated with the treatment such as local inflammation due to an inadequately placed or polished restoration, and/or oral lichenoid reactions that are in direct vicinity to the study restoration, will be documented in detail and the patient affected will be excluded from the study. In this case, the restoration will be replaced by another material as soon as possible. In addition, a restoration that fractures due to a mechanical failure of the material will also be replaced as soon as possible. It is possible to have an irreversible pulpitis develop after placement of the restoration, as often times happens during routine dental treatment. In this case, the subject will be excluded from the study and will have to continue with the appropriate treatment at the dental office of their choice at their own expense.

Biostatistical analysis

Study design

The goal of this clinical trial is to show that Venus Pearl (a development based on the material "Venus Diamond", Heraeus Kulzer, Hanau – Germany) has a better score than the commercially available control material (Filtek Supreme XTE, 3M/ESPE, Seefeld – Germany and Filtek Supreme Ultra, 3M/ESPE, USA) for the restoration of class II-cavities. Patients older than 18 who show an interproximal (Class II) carious lesion or an existing defective restoration requiring therapy on premolars or molars will be included.

For the determination of the superior outcomes of both fillings a pre-specified evaluation scheme will be used.

The assessment of the replacement will be performed at four time points (1 week, 6 months, 12 months and 24 months after replacement). For the primary analysis the score will be considered 24 months after the replacement.

The primary endpoint will be a mean score calculated as following: There are three aspects to be assessed: aesthetic, functional attribute and biological parameters. For each aspect there are respectively four categories where each has to be assessed on a scale from 1 to 5. Thereby 1 means clinically excellent, 2 means clinically good and 3 means clinically disappointing. This assessment form is given in FDI World Dental Federation (J Adhes dent 9 (1), 121 – 147 (2007)). For each

patient the points of the 12 different evaluation criteria (four categories in the three parts) will be summed up resulting in a score that ranges from 12 to 60.

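### The primary ANOVA has no patient term although one patient may supply up to four of the 180 restorations, so the confidence interval that decides success ignores within-patient correlation

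*Combined protocol and SAP*

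**What the plan says.** The sample is counted in restorations. *General information* plans "90 comparable cavities per Institution (180 total), randomization", that is 90 per material and 45 per material and site. *Recruitment of patients* adds: "Each patient will be eligible to receive up to four restorations, with either a test or a control material".

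The primary analysis (*Description of the primary analysis and key secondary analysis*) is an ANOVA of the 24-month score. On its terms the plan says: "Here, center, tooth type and treatment will be incorporated as covariables". The trial succeeds if the 95% confidence interval for Venus Pearl minus Filtek Supreme lies below 0. The same section later announces mixed models as a sensitivity analysis, without naming an outcome or a random effect.

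On allocation, *Randomization, stratification and blinding* says "Restorations will be distributed evenly between the control and the experimental groups using randomization lists" and "stratification with the strata premolar and molar will be performed in the randomization process". It also ties randomization to a scheduled visit and files the allocation against the patient ID.

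Elsewhere the unit is the patient. *Biostatistical analysis – Study design* says that for each "patient the points of the 12 different evaluation criteria (four categories in the three parts) will be summed up", and the ITT population is defined as all randomized patients.

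**The concern.** Restorations in one mouth share hygiene, diet and occlusion, so their scores are likely to be correlated. An ANOVA with only center, tooth type and treatment treats them as independent, and its interval is the only success criterion. The direction of the error depends on allocation:

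- (a) If the restorations of a patient or of a visit share a material, the interval is too narrow and false superiority exceeds 2.5%.
- (b) If materials are split within patients, the interval is too wide.
- (c) If each restoration is randomized independently, the error is about nominal and the ANOVA wastes precision.

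The text leans toward (c), because it distributes restorations and stratifies on a tooth-level factor. The visit sentence, however, leaves one material per visit possible, and the either/or wording on up to four restorations can be read per patient or per restoration. A reader therefore cannot tell which case applies.

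The wording on units is a separate conflict. A score per patient has no single tooth type or material when the patient has mixed teeth or materials, and no rule for combining restorations is given.

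**Working it through.** **Inputs from the document.** 45 restorations × 2 materials × 2 sites = 180, which is consistent. A patient may have up to four. The success rule is a 95% interval below 0, so the nominal chance of false superiority is 2.5%. No effect size, SD, power, number of patients or within-patient correlation (ICC) is stated, so there is no power figure to reproduce.

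**Assumptions.** ICC 0.1 to 0.5. Patients with 1/2/3/4 restorations:

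- Mix A, 70/20/5/5%: mean 0.70 + 0.40 + 0.15 + 0.20 = 1.45, so 180/1.45 ≈ 124 patients.
- Mix B, 40/30/20/10%: mean 0.40 + 0.60 + 0.60 + 0.40 = 2.0, so 90 patients.

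**One material per patient, by formula.** With m restorations per patient, the design effect is DE = 1 + ICC × (Σm²/Σm − 1), and false superiority = 1 − Φ(1.96/√DE).

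- Mix A: Σm²/Σm = 2.75/1.45 = 1.897, so DE = 1 + 0.897 × ICC.
- Mix B: Σm²/Σm = 5.0/2.0 = 2.5, so DE = 1 + 1.5 × ICC.

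| Mix | ICC | DE | Effective size (180/DE) | False superiority |
|---|---|---|---|---|
| A | 0.1 | 1.09 | 165 | 3.0% |
| A | 0.5 | 1.45 | 124 | 5.2% |
| B | 0.1 | 1.15 | 157 | 3.4% |
| B | 0.5 | 1.75 | 103 | 6.9% |

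Upper bound: four restorations in every patient, one material per patient and ICC 0.5 give DE = 1 + 3 × 0.5 = 2.5, and 1 − Φ(1.96/1.581) = 10.8%.

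**Simulation of the specified ANOVA under no effect.** 180 restorations, 90 per center, tooth type drawn per restoration, 4000 runs per cell. There were 30 cells: two mixes, ICC 0.1/0.3/0.5 and five allocation rules, two of which are forms of independent allocation. False superiority is taken as half the two-sided error; the Monte Carlo SE of the two-sided error is about 0.35 points near 5%. Ranges run from ICC 0.1 to 0.5, except that the last row covers all its cells.

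| Allocation | Mix A | Mix B |
|---|---|---|
| One material per patient | 3.0–5.5% | 3.5–6.4% |
| One material per visit (at most two restorations per visit assumed) | 2.5–3.6% | 2.8–4.2% |
| Alternated within patient | 2.4–1.1% | 2.0–0.8% |
| Independent per restoration (blocked or simple) | 1.9–2.6% | 1.9–2.6% |

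In interval width, sharing per visit makes the interval too narrow by 2–8% (A) or 2–11% (B). Splitting within patients makes it too wide by 2–14% (A) or 4–23% (B).

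**Random-intercept model on the same data.** A REML model with a patient intercept had a two-sided error of 4.2–5.8% in all 30 cells, against 1.6–12.7% for the ANOVA. Separate runs gave 4.0–6.5%, and up to 6.3% with an added visit effect.

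**Precision under independent allocation.** With known variance components, a patient effect cuts the variance of the treatment estimate by about 1% at ICC 0.1, 6% (A) to 10% (B) at ICC 0.3, and 17–18% (A) or 24–26% (B) at ICC 0.5. Where the ANOVA has 80% power, power becomes Φ((1.96 + 0.84)/√(1 − cut) − 1.96): 80.4% at a cut of 0.01, 86.8% at 0.17 and 90.3% at 0.26.

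**The case against.** The best defence is that on the reading the text favours, independent allocation of each restoration, validity is not harmed. The visit sentence more naturally says when randomization is triggered than which restorations share a material. Patient-level allocation fits badly with a premolar/molar stratum when one patient has both. This stands, and it is why the point is not a claim that type I error is inflated. It does not settle the allocation rule, because the either/or wording on up to four restorations and the filing by patient ID keep a patient-level reading open.

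The size rests on an assumed ICC and an assumed patient mix. That also stands: the result runs from conservative through nominal to inflated.

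The precision gain uses known variance components. With the ICC estimated, the cut is about 0% at ICC 0.1 (−0.2 to 0.7%), 4–10% at 0.3, and 15–16% (A) or 24–26% (B) at 0.5. At low ICC the mixed model gains essentially nothing, but it loses essentially nothing either.

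The exclusion "Rampant or extensive caries present" makes four restorations in every patient unlikely. It does not rule this out, since defective existing restorations are also eligible. The 10.8% is an upper bound only.

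The plan already mentions mixed models, and they may be meant to cover the primary score. As an unspecified sensitivity analysis they do not decide success.

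Finally, if the per-patient wording is literal, clustering disappears. The 180 would then no longer be independent scores, and tooth type and material would be undefined for patients with mixed restorations.

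**Conclusion.** The concern holds. That the deciding model lacks a patient term is certain from the text. The consequence is conditional on the allocation rule, the ICC and the number of restorations per patient. Under the assumptions above, false superiority lies between 0.8% and 6.9% depending on allocation, against a nominal 2.5%. On the favoured reading it is about nominal, and the cost is precision: negligible at ICC 0.1, and roughly 15–26% of the variance of the treatment estimate at ICC 0.5. With one restoration per patient nothing changes. A patient random intercept keeps the two-sided error near 5% under every allocation rule examined. The plan should be changed, but this is not a defect that by itself invalidates the trial.

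**What to change.** 1. Define the restoration as the unit of scoring and of the ITT analysis set, and align the per-patient wording with it.
2. State the randomization unit actually used, including what happens when one patient or one visit has several restorations. This describes the procedure and does not change it.
3. Make the primary analysis a linear mixed model with treatment, center and tooth type as fixed effects and patient as random intercept, fitted by REML with Kenward-Roger or Satterthwaite degrees of freedom. Base the success interval on it and keep the plain ANOVA as sensitivity analysis.

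The cost is SAP wording. Mixed models are already foreseen, but the model for the primary score has to be written out. The downside is that the interval may widen if patients mostly receive one material; in that case the wider interval is the valid one.

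### The primary ANOVA leaves out cavity depth and indication, which are assessed before allocation; adjusting for them is a valid, cheap option that may gain a little precision

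*Combined protocol and SAP*

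**What the plan says.** The section on the primary and key secondary analysis states that "an ANOVA will be performed 24 months after restoration" and lists the model terms: "Here, center, tooth type and treatment will be incorporated as covariables". The decision rests on one interval: "The study is successful if the 95 % confidence interval for the treatment effect (Venus Pearl – Filtek Supreme) is below 0".

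The section on randomization, stratification and blinding explains the two covariates. For tooth type, "stratification with the strata premolar and molar will be performed in the randomization process"; for site, "In addition randomization will be stratified by center". The model is therefore treatment plus the two strata. The same section says that allocation is central and follows admission.

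The inclusion criteria require a depth reading for every tooth: "The maximum cavity depth determined by the radiograph will be D2 (Tyas classification". They admit two indications, a "carious lesion or an existing defective class II restoration requiring restorative therapy". The exclusion criteria add a limit on cusps: "Replacement of more than one cusp indicated".

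The plan does not say that depth grade or indication is recorded as an analysis variable, or that either predicts the score.

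**The concern.** A site cannot admit a tooth without reading its depth and deciding whether it has a new lesion or a defective restoration. Because admission precedes allocation, both are baseline characteristics in the strict sense: the assigned material cannot influence them. The 1-week assessment that the protocol calls baseline does not have this property, since it follows placement.

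New lesions and replacements, at depths up to D2, all enter the same comparison. If these characteristics are related to the 24-month score, their contribution stays in the error term and widens the interval on which success depends. Any chance difference between arms in the mix of cavities also goes uncorrected. The plan gives no power calculation, SD or target difference, so no margin of precision is documented.

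Pre-specification matters because covariates added after outcomes are known would be open to challenge.

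**Working it through.** **The plan's own figures.** Under general information, 45 restorations per arm per site gives 2 × 45 = 90 per arm and 2 × 90 = 180 in total. These agree. No power, SD, effect size or dropout allowance is stated, so 180 cannot be derived from the documents.

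**Inputs**
- From the plan: N = 180, 90 per arm, and a model with intercept, treatment, center (2 levels) and tooth type (2 levels). Residual degrees of freedom: 180 − 4 = 176.
- Assumed: two added single-degree-of-freedom terms, leaving 174. The documents do not give the number of depth grades; more grades would cost more.
- Assumed: R², the share of residual variance (after center and tooth type) explained by the two added terms. No value is given, so a range is shown.
- Assumed: independent restorations.

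**Formulas**
- Variance ratio V = (1 − R²) × 176/174
- Interval width ratio = √V
- Equivalent change in restorations = 180/V − 180
- Power, from an assumed anchor. With 90 per arm and two-sided 5%, a difference of (1.960 + 0.842) × √(2/90) = 0.418 SD has 80% power under the planned model. With the added terms, power = Φ(2.802/√V − 1.960).

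| Assumed R² | V | Width ratio | Change in width | Equivalent restorations | Power (from 80%) |
|---|---|---|---|---|---|
| 0 | 1.0115 | 1.0057 | +0.6% | −2 | 79.6% |
| 2% | 0.9913 | 0.9956 | −0.4% | +2 | 80.3% |
| 5% | 0.9609 | 0.9803 | −2.0% | +7 | 81.5% |
| 10% | 0.9103 | 0.9541 | −4.6% | +18 | 83.6% |
| 20% | 0.8092 | 0.8996 | −10.0% | +42 | 87.6% |

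**Break-even.** V = 1 when R² = 1 − 174/176 = 1.1%. Below that, adjustment widens the interval slightly.

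**What R² might be.** Two balanced binary factors that each shift the score by δ SD give R² ≈ 2 × 0.25 × δ². For δ = 0.2, 0.3 and 0.5 this is 2%, 4.5% and 12.5%. Modest effects therefore sit in the upper rows of the table.

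**Chance imbalance.** For a 50/50 factor, the between-arm difference in prevalence has SD √(2 × 0.25/90) = 7.5 percentage points, so differences up to about 15 points are ordinary. If the factor shifts the score by 0.3 SD, a 15-point imbalance moves the estimated difference by 0.15 × 0.3 = 0.045 SD. The standard error is √(2/90) = 0.149 SD, so the shift is about 0.3 of a standard error.

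**The case against.** The strongest reply is that nothing is wrong with the plan here. The model contains treatment and both strata. Randomisation keeps the estimate unbiased without further covariates, and the confidence interval already allows for chance imbalance in unstratified factors. Almost any trial could be told to add another eligibility variable. All of this stands, and it is why the point is only a suggestion.

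Several stronger readings are tempting, and the documents do not support them:

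- *The omission does lose precision.* A reader might infer this, but it depends on R². The documents give no SD, no R² and no evidence that depth or indication predicts the 12 to 60 score. Below an R² of about 1.1% there is a small loss from adjusting.
- *The plan itself treats these factors as prognostic, because it limits them and asks for comparable cavities.* The limits stand among criteria on pulp vitality and suitability for a direct adhesive restoration, so they can equally be read as treatment suitability. The D2 ceiling also narrows the variation in depth, which makes a large R² less plausible.
- *Eligibility fixes these values for the analysis.* It requires them to be judged. It sets only an upper limit on depth, admits both indications, and does not say that the values are recorded in analysable form.
- *Cusp replacement should be adjusted for as well.* The exclusion concerns whether more than one cusp is indicated for replacement. Whether a cusp was in fact replaced is not shown to be settled before allocation, and adding the term only if enough restorations have it would make the primary model depend on the data.

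The reply does not remove the asymmetry: about 0.6% wider at worst with two added terms, against a gain of several percent if the factors matter moderately.

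**Conclusion.** The point holds as an optional gain in efficiency. Depth grade and indication are legitimate pre-allocation covariates that neither the stratification nor the primary model controls. Leaving them out does not bias the treatment effect or invalidate the test.

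Over the assumed R² of 0 to 20%, the interval changes by between +0.6% and −10%. With modest effects of 0.2 to 0.3 SD per factor, R² is about 2% to 4.5% and the narrowing is at most about 2%. Only at R² of about 10% or more does the gain become material.

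The figures treat the 180 restorations as independent. The protocol allows up to four per patient and the primary ANOVA has no patient term. That is a separate matter which could change the standard error by more than these covariates, but its size cannot be judged because the documents give neither the within-patient correlation nor the number of restorations per patient.

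**What to change.** Pre-specify the primary model as treatment, center, tooth type, indication (new carious lesion or defective restoration) and radiographic depth grade. The last two should be the values determined at eligibility, before allocation, and captured in the CRF. Use the same covariates when the score is compared at the other visits. State beforehand how depth is graded when the indication is a defective restoration, which the documents leave open. Do not add a term for cusp replacement.

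The cost is a short SAP amendment, two eligibility values per tooth in the CRF, and about two degrees of freedom out of 176 (more if depth has more than two grades). If neither factor is prognostic, the interval widens by about 0.6% with two added terms.
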